9.3 Demographic and Baseline Characteristics

Summary statistics will be provided per treatment group for demographic (e.g., age, height, weight, body mass index [BMI], race, gender) and other initial subject characteristics (e.g., medical history, concomitant diseases) will be provided per treatment group and for the total group. The ITT population will be used for the summaries.

9.4 Analysis Populations

The following analysis populations will be defined for the study:

The intent-to-treat (ITT) population will include all randomized patients. Patients will be analyzed according to their assigned treatment arm. All efficacy analyses will be completed in the ITT population.

The safety population will include all patients who receive study treatment. Patients will be analyzed according to actual treatment received. All safety analyses will be completed in the safety population.

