1 SYNOPSIS

Title	A Phase 2 Randomized, Double Blinded, Placebo Controlled Study of Oral Favipiravir Compared to Current Standard of Care in Subjects with Mild or Asymptomatic COVID-19
Design	
This is a Phase 2 Double Blinded, Placebo Controlled Study evaluating the efficacy, safety and pharmacokinetics of favipiravir in adult subjects with PCR-positive, mild or asymptomatic COVID-19 infections. The study is a multicenter trial that will be conducted in up to 5 sites nationwide.
 
Subjects will be randomized to receive either favipiravir + current Standard of Care (SOC) or placebo + SOC.
 
For those subjects in the favipiravir + SOC arm, the dose regimen will be 1800 mg BID favipiravir on the first dose (day 1) followed by 800 mg BID for the next 9 days (days 2-10).
 
NOTE: 600 mg BID for subjects with Child-Pugh A liver impairment on days 2-10.
 
Subjects in the SOC arm will receive placebo.
 
The total anticipated duration of the study for each patient is 28 days.

Objectives	
Primary Objective
 
To evaluate the efficacy of oral favipiravir plus SOC compared with placebo plus SOC in reducing the duration of shedding of SARS-CoV2 virus in patients with mild or asymptomatic COVID-19.
 
Secondary Objectives
 
 1. To evaluate the efficacy of oral favipiravir compared with placebo in reducing the onset or duration of symptoms, hospitalizations, or ED visits in patients with mild or asymptomatic COVID-19. 2. To assess the safety and tolerability of favipiravir in this subject population. 3. To assess the development of antibodies against SARS-CoV-2 4. To evaluate any changes in the PK profile of favipiravir and its major metabolite M1 in this subject population
Endpoints	
Primary Endpoint:
 
Time until cessation of shedding of SARS-CoV-2 virus, defined as the time in days from randomization to the first of two consecutive negative RT-PCR results of self-collected nasal swabs.
 
Secondary Endpoints
 
 1. Nucleic acid (RT-PCR) from oropharyngeal swabs collected on Days 1, 5, 10, and 28

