	
mg/day). Then maintenance dosing of 800 mg BID (1600 mg/day) from Day 2 (beginning 18-24 hours after the loading dose on Day 1).
 
 • Patients with Child-Pugh liver impairment of grade A will have their maintenance dose decreased to 600 mg BID • The total duration of treatment is expected to be 10 days.

Duration of Study Participation
	
The total anticipated duration of the study for each patient is up to 28 days.

Statistical Methods
	
To address our primary objective, time until viral shedding cessation will be compared between the two treatment arms using a two-sided Wald test derived from a Cox proportional hazards model adjusted for age and sex and stratified by site. The test will be performed at the two-sided $\alpha = 0.05$ level of significance. The hazard ratio for shedding cessation will be estimated, along with its 95% confidence interval, from a Cox proportional hazards model. If the proportional hazards assumption is not met, we will consider an extended Cox model that relaxes the proportional hazards assumption. The log rank test will also be performed.
 
The distribution of viral shedding cessation will be estimated using the Kaplan-Meier method, and Kaplan-Meier curves will be presented for each treatment arm. Time to shedding cessation along with 95% confidence intervals will be presented for each treatment arm.
 
The rate of hospitalizations and ED visits will be estimated along with 95% confidence intervals by each arm. In addition, we will compare between arms the time to each of respiratory failure, hospitalization or deaths and the corresponding composite of all such events using Kaplan-Meier methods. The frequency of adverse events and serious adverse events will be tabulated by type and by treatment arm. AEs will be compared by arm using the Chi-squared test or Fisher’s exact test, as appropriate, in the safety analysis set.
 
An interim analysis for safety and overwhelming efficacy will be performed once 50% of patients have 24 hours of follow-up complete. Enrollment will pause once 50% of patients have received treatment and will remain paused until the DSMC makes their recommendation after their safety review.

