7.1 Day 1 (PRE-DOSE)

- Obtain informed consent.
- Verify eligibility per the inclusion and exclusion criteria. (See Sections 5.1 and 5.2)
 - Review and record medical history, including tobacco use, to ensure there are no exclusionary illnesses.
 - Review and record concomitant medications for possible prohibited medications. (See Section 6.7)
- If subject is female of child-bearing potential and meets inclusion criteria 11.c, obtain urine pregnancy test and proceed if result is negative.
- Measure and record vital signs (BP, HR, Temp, Resp).
- Collect and record SPO2 by Finger Sensor
- Perform Physical exam (may be done by the Principal Investigator or their designee)
- Complete baseline symptom survey to establish severity of symptoms (if present)
- Collect oropharyngeal swab for virologic testing (RT-PCR) and resistance analysis.
- Collect two nasal swabs for antigen testing and molecular viability testing.
- Collect blood samples for
 - Uric acid
 - CRP
 - Hematology and clinical chemistry laboratory analyses (samples collected within 48 hours of enrollment are acceptable):
 - Resistance analysis
 - Optional: Antibodies to SARS-CoV-2.
 - Optional: Biobanking
 - Optional: Pre-dose PK

- Perform subject randomization (via EDC) to establish treatment arm (favipiravir + SOC or placebo + SOC).
- Explain in home procedures for the study (self-sampling of nasal swabs, temperature, SPO2, completing the daily questionnaire and the optional collection of stool sample).
- Provide supplies to research subject and review the calendar of return visits.
- Optional: Explain that stool sample from first bowel movement after enrollment should be collected in Zymo fecal tube and brought back to Day 5 follow-up visit. If the first bowel movement sample cannot be collected, it is permitted to collect a subsequent bowel movement sample.

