9 STATISTICAL METHODS

Complete details of all statistical analyses, including methods for handling missing data, will be included in a formal statistical analysis plan (SAP), to be completed as soon as possible after study initiation.

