9.2 Sample size justification

Approximately 180 patients will be enrolled.

Assuming 1:1 randomization and the use of a two-sided log rank test at the $\alpha=0.04999$ level of significance for the final analysis, 79 events will provide 80% power to detect a hazard ratio of 2.03. This leaves $\alpha=0.00001$ to check for overwhelming efficacy after 60 participants have completed 24 hours of follow-up. Assuming the control and treatment arm median cessation of shedding is 14 and 7 days, respectively, a two-month accrual period, a two-week follow-up period after randomization of the last patient, and a drop out of 10% in the control arm, it is estimated that the total sample size required to achieve 79 events is 120 (60 patients in each arm). We assume 33% of patients will test negative for SARS-CoV-2 virus by RT-PCR on Day 1, thus the total sample size required to be randomized is 180 ($120/0.67$). The assumption of 33% is based on calculations performed after the DSMB recommended a sample size re-estimation to account for the patients who test negative at baseline and do not contribute meaningfully to the primary analysis.

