10 INTERIM ANALYSIS

An interim analysis for safety and overwhelming efficacy will be performed once 50% of patients have 24 hours of follow-up complete. Enrollment will pause once 50% of patients have received treatment and will remain paused until the DSMC makes their recommendation after their safety review. The DSMC will meet one or two days after enrollment is paused to review the safety data collected within the first 24 hours of follow-up on all enrolled patients. We additionally expect blood count labs collected at day 5 to be available in approximately 25% of patients at the time of the DSMC review.

The DSMC will also review the efficacy data on all randomized participants at this meeting. The interim efficacy analysis will use the same methods as are planned for the final analysis using the ITT analysis. Based on the results of the interim analysis, the DSMC will either recommend to the sponsor to terminate the study for overwhelming efficacy ($p < 0.00001$ at the interim analysis),

terminate the study for safety concerns, modify the study, or continue the study as planned. No formal stopping rules for futility are planned.

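### Section 9.2 sizes the trial as if Day 1 RT-PCR negatives add nothing, but the primary test includes them; if the expected 33% stay nasal-negative, power falls from about 90% to about 71–75%, below the stated 80%

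*Combined protocol and SAP*

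**What the plan says.** - **Sizing (9.2).** The plan finds 120 patients sufficient, then states "We assume 33% of patients will test negative for SARS-CoV-2 virus by RT-PCR on Day 1" and inflates to 180. The reason given is a re-estimation prompted by the DSMB to allow for "the patients who test negative at baseline and do not contribute meaningfully to the primary analysis".
- **Analysis set (9.4).** ITT is everyone randomized, with no condition on Day 1 PCR, and "All efficacy analyses will be completed in the ITT population". The only other set defined is the safety population; MITT appears in the abbreviation list but is not defined.
- **Interim (10).** "The interim efficacy analysis will use the same methods as are planned for the final analysis using the ITT analysis".
- **Endpoint (Synopsis).** Time to cessation of shedding is "defined as the time in days from randomization to the first of two consecutive negative RT-PCR results of self-collected nasal swabs".
- **Test (Synopsis).** A two-sided Wald test from a Cox model adjusted for age and sex and stratified by site; also "The log rank test will also be performed".
- **Day 1 specimens.** Section 7.1 lists, before dosing, "Collect oropharyngeal swab for virologic testing (RT-PCR) and resistance analysis". The primary swab is the self-collected nasal one. Section 9.1 words the hypotheses in terms of oral shedding.

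Section 9 leaves full analysis details to a later SAP. No section says how a Day 1 negative is coded, which swab the 33% refers to, or how tied event times are treated.

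**The concern.** The sizing and the analysis describe different populations. Section 9.2 treats Day 1 negatives as absent; 9.4 and 10 count them. Counting them is not neutral. By the endpoint definition, a patient negative on the first two nasal swabs has the event at time zero whichever arm was assigned, because there is no shedding left to shorten. These events add variance and no signal, so the estimated hazard ratio moves toward 1 and the test loses power.

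At stake are the power that the extra 60 patients were added to protect and the meaning of the reported hazard ratio. A coding choice left open until data exist could move the estimate between about 1.5 and 2.0.

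**Working it through.** **Inputs.** From 9.2: medians of 14 and 7 days, 10% control dropout, 33% Day 1 negative, 120 inflated to 180, two-month accrual with two weeks after the last patient. From 9.5: 1:1 allocation. From 8.1: nasal swabs on Days 1–10, 14, 21 and 28. Assumed: exponential times, the 33% is the nasal swab, time-zero events are kept, two-sided 0.05, no covariates or site strata.

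**1. The plan's own figures.** 120/0.67 = 179.1, so 180 reproduces. The stated 80% does not. By Schoenfeld, 79 events at HR 2.03 give Z = 0.708 × √(79/4) = 3.15, hence power Φ(3.15 − 1.96) = 88% (Freedman: 86%). For 80%, 63 events suffice (Freedman: 68). This is a separate discrepancy; it partly explains why the positives-only power below exceeds 80%.

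**2. Hand calculation.** Simulation gives about 88 events in Day 1 positives by Day 28.

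- Positives only: information 88 × 0.25 = 22; Z = 0.708 × √22 = 3.32; power 91%.
- All randomized, Cox with Efron ties: 60 time-zero events add 60 × 0.25 = 15. Then ln HR = 22 × 0.708/37 = 0.42, so HR 1.52. Z = 22 × 0.708/√37 = 2.56; power 73%.
- All randomized, log rank: the tied events add 60 × 0.25 × (120/179) = 10.1. Z = 22 × 0.708/√32.1 = 2.75; power 79%.

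This treats every risk set as evenly split, so it runs a little high.

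**3. Simulation on the swab schedule**, two consecutive negatives required, 5,000–8,000 trials per scenario (Monte Carlo SE at most √(0.25/5,000) = 0.7 points). Power is Cox–Efron / log rank. Transient Day 1 negatives were given the same shedding distribution as positives.

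| Scenario (N = 180, Day 28, unless stated) | Day 1 positives only | All randomized |
|---|---|---|
| 33% negative, all persist | 90%/90%; 88 events, HR 2.03 | 71%/75%; 147 events, HR 1.52 |
| Same, with 9.2 timing | 88%/88%; 83 events | 66%/71%; 142 events, HR 1.50 |
| 90% of negatives persist | – | 76%/78% |
| 75% persist | – | 83%/84% (9.2 timing: 78%/80%) |
| 50% persist | – | 90%/90% (9.2 timing: 86%/86%) |
| 20% negative, all persist | 95% | 88%/88% (9.2 timing: 84%/85%) |
| True HR 1.75, 33% negative, all persist | 74%/74% | 53%/56% |
| N = 120 in total, 33% negative, all persist | – | 54%/58% |
| No treatment effect | – | rejects 4.8%/5.0% |

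**4. Sensitivity.** With Breslow ties, the first row's all-randomized power is 65%. With exactly recorded event times instead of the swab grid, power over 28 days falls from 92–93% to 76–87%. If software drops time-zero records, power equals positives-only, but the analysis is then not the ITT of 9.4.

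**5. Does stratifying by Day 1 status repair ITT?** In a stratum where all 60 patients have the event at time zero, the log-rank variance contains the factor (60 − 60)/(60 − 1) = 0, so the stratum drops out and stratified log-rank power is 91%. The Efron information there is still 60 × 0.25 = 15, so a stratified Cox model stays diluted: HR 1.53, power 77–78% (Breslow: HR 1.47, 69–70%).

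**The case against.** The 71–75% is the unfavourable end of a range. It needs the 33% to be nasal, every Day 1 negative to be negative again on Day 2, and time-zero events to be kept; the documents establish none of these. Everyone had a positive test within 72 hours of consent, so some single negatives may be transient. All-randomized power returns to 80% at about 80% persistence with follow-up to Day 28, or about 70–75% persistence with the 9.2 timing. With 25% negative, all persistent, it is 81–83%. The plan's benchmark is 80%, not 90%, so the headline shortfall is 5–9 points. Type I error holds, ITT errs toward the null, and going from 120 to 180 does raise ITT power.

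Those figures stand, and they make the loss conditional. They do not remove the contradiction. Full persistence is what 9.2 itself presumes: a Day 1 negative who then sheds virus does contribute to the analysis. On that premise the ITT test misses 80% under either follow-up assumption.

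Two further points stand. Section 7.1 already lists two pre-dose nasal swabs, for antigen and molecular viability testing; the plan does not say whether they yield an RT-PCR result. And no power was computed for the interim, where the threshold is p<0.00001; changing Section 10 is for consistency with the final analysis.

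**Conclusion.** The concern holds. Section 9.2 and Sections 9.4 and 10 cannot both stand. On the plan's own 33% and medians, with nasal-negative patients who stay negative and are kept as events, the primary test has about 71% (Cox) to 75% (log rank) power with follow-up to Day 28, or 66–71% with the 9.2 timing. Day 1 positives alone would give about 90% or 88%. The hazard ratio shrinks from about 2.0 to about 1.5. The loss is small if half the negatives are transient or only 20% are negative. It rests on exponential shedding times and omits covariates and site strata. Validity under the null is intact; what suffers is power and interpretation. Because the primary test is affected and its coding is undefined, this should be settled before unblinding. Confidence is high in the inconsistency; the size of the loss depends on persistence and coding.

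**What to change.** Before unblinding, amend 9.4, 9.6 and 10:

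- **Primary and interim efficacy set:** all randomized patients with a positive Day 1 RT-PCR, analysed as randomized. Name the swab.
- **Baseline specimen:** from now on, take the Day 1 nasal swab before the first dose. Check first whether the nasal swabs already listed in 7.1 can supply the result. For enrolled patients whose Day 1 nasal swab is missing or post-dose, fix a blinded rule using a pre-dose result, such as the oropharyngeal RT-PCR in 7.1.
- **Coding:** state how Day 1 negatives enter the time-to-event data and which tie method is used.
- **Full ITT as supportive:** stratify by Day 1 PCR status and use a stratified log-rank test or exact discrete ties, since a stratified Cox model with Efron ties remains diluted.
- **Wording:** in 9.1, refer to shedding by self-collected nasal swab.

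If the sponsor prefers ITT as primary, 9.2 must be re-sized and the coding stated. Scaling Z with √N from the Day 28 figures: 180 × (2.80/2.63)² = 204 for the log rank (75% power) and 180 × (2.80/2.51)² = 224 for Cox (71%), so roughly 205–225 patients if all negatives persist.

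**Cost.** Wording plus swab timing; no extra visits. The primary set is no longer everyone randomized, and arm sizes may differ slightly because PCR status was not a randomization stratum. Timing cannot be changed for patients already enrolled. Coming after a DSMB-prompted re-estimation, the change must be documented as made blind to outcome by arm.

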9.5 Stratification, Subgroup Analysis and Pooled Analysis

Following consent, those subjects meeting all entry criteria will be randomized in a 1:1 ratio

Treatment Arm: favipiravir + SOC

Control Arm: placebo + SOC

Randomization will be stratified by age (≥ 50 and < 50 years old) and sex.

Members of the same household may participate in the study as long as the inclusion and exclusion criteria are met. Because this is a double-blind, placebo-controlled trial, subjects from the same household will be randomized just as any other subject.

9.6 Efficacy Endpoint Analysis

Descriptive analyses

Descriptive statistics (proportions for categorical variables, means, medians, standard deviations, and interquartile ranges for continuous variables) will be reported for all key patient variables, including baseline and demographic characteristics, use of medications, compliance, and study completion status. Data that are missing on key patient characteristics and the outcome will be fully described, including any patterns of missingness (i.e., any relationships between missingness of a variable and patient characteristics).

A CONSORT diagram displaying the number of patients screened, eligible, and consented along with reasons for ineligibility will be provided. Graphical tools such as histograms, boxplots, and scatterplots will be created to assess quality of data and to display patterns over time.

Primary efficacy analysis

Time until shedding cessation will be compared between the two treatment arms using a Cox proportional hazards model adjusted for age and sex and stratified by site. The test will be performed at the $\alpha = 0.05$ level of significance. The hazard ratio for shedding cessation will be estimated, along with its 95% confidence interval, from a Cox proportional hazards model. If the proportional hazards assumption is not met, we will consider an extended Cox model that relaxes the proportional hazards assumption.

The distribution of shedding cessation will be estimated using the Kaplan-Meier method, and Kaplan-Meier curves will be presented for each treatment arm. Time to shedding cessation at the end of the study period along with 95% confidence intervals will be presented for each treatment arm.

Secondary efficacy analyses

The distribution of cessation of symptoms will be estimated using the Kaplan-Meier method, and Kaplan-Meier curves will be presented for each treatment arm. Time to cessation of symptoms at the end of the study period along with 95% confidence intervals will be presented for each treatment arm. The hazard ratio for cessation of symptoms will be estimated, along with its 95% confidence intervals, from a Cox proportional hazards model. Time to cessation of symptoms will be determined by analysis of daily questionnaires. Resolution of symptoms requires that symptoms are mild or absent for at least 24 hours.

The number of hospitalizations, emergency department visits, incidence of respiratory failure, deaths, and proportions of subjects alive, not hospitalized, and free of respiratory failure will be estimated for each arm, with 95% confidence intervals. Respiratory failure is defined as the need for mechanical ventilation, ECMO, non-invasive ventilation, or high-flow oxygen

Our analyses will use multiple imputation methods that assume data are missing at random by including all baseline characteristics, treatment assignment, and reasons for missingness in the imputation model. This approach will be applied to any analysis involving endpoints or key variables where any missing data occurs in order to adhere to the ITT principle. Assumptions regarding missingness will be addressed in sensitivity analyses.

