	
m. New loss of taste or smelln. Abdominal paino. Rash 
The date of onset of the first of the above symptoms will be documented.
 
p. If asymptomatic, initial diagnosis obtained no more than 72 hours from initial swab to the time of commencing informed consent 
3. Subject or their legal representative understands the requirements of the study and provides written informed consent prior to undergoing any treatment-related procedures.4. If male, subject must fulfill one of the following criteria:
a. Be sterile (e.g., have had a vasectomy at least 6 months prior to Day 1 dosing), OR,b. Agree not to donate sperm during the study and for seven days following the last dose of study medication, AND,c. Agree to strictly adhere to the following contraceptive measures during the study and for seven days following the last dose of study medication:
i. Abstain from sexual intercourseii. Use a condom during sexual intercourse with a female of child-bearing potential. In addition, the female partner must use another form of contraception (e.g. intrauterine device [IUD], diaphragm with spermicide, oral contraceptives, injectable progesterone, or subdermal implants).5. If female, subject must fulfill one of the following criteria:
a. Be unable to bear children (have not had a period for ≥ 12 consecutive months, have had her uterus or ovaries removed, or have had a tubal ligation), OR,b. Must ensure that their male partner is incapable of fathering a child (e.g., has had a vasectomy at least 6 months prior to study entry), OR,c. If she is of childbearing potential will strictly adhere to the following contraceptive measures during the study and for seven days following the last dose of study medication:
i. Abstain from sexual intercourse, OR,ii. Must ensure that their male partner agrees to use a condom during sexual intercourse and agree to use an approved method of contraception (e.g., IUD, diaphragm with spermicide, oral contraceptives, injectable progesterone, or subdermal implants).
--	---

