3 DESIGN

3.1 Study Design

This is a Phase 2 Double Blinded and Placebo Controlled Study evaluating the safety, pharmacokinetics, and efficacy of favipiravir in adult subjects with PCR-positive, asymptomatic, or mild COVID-19 infections.

Subjects will be randomized to receive either favipiravir + current local Standard of Care (SOC) or placebo + SOC. SOC at Stanford is defined as methods Stanford University Healthcare is using for COVID-19 patients at the time of study initiation. Each site's local SOC to be defined and shared with Sponsor prior to study initiation.

For those subjects in the favipiravir + SOC arm, the dose regimen will be 1800 mg BID favipiravir on the first dose (day 1) followed by 800 mg BID for the next 9 days (days 2-10). NOTE: 600 mg BID for subjects with Child-Pugh A liver impairment on days 2-10.

Subjects in the SOC arm will receive placebo. The total anticipated duration of the study for each patient is 28 days.

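### The primary Cox model leaves out baseline symptom status and time since symptom onset, an efficiency gain of unknown size that could be had at almost no cost

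*Combined protocol and SAP*

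**What the plan says.** Section 9.6 fits the primary Cox model "adjusted for age and sex and stratified by site"; the synopsis gives the same model. Age and sex are also the two randomization factors (section 9.5: "Randomization will be stratified by age", cut at 50 years, and by sex). Symptom status is not a randomization factor.

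The design mixes illness stages. Section 3.1 enrolls people with "PCR-positive, asymptomatic, or mild COVID-19 infections". The primary endpoint in the synopsis counts days from randomization. Eligibility limits the age of the positive swab to 72 hours but puts no limit on symptom duration.

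Two relevant baseline items are to be collected. Section 7.1 lists, before dosing, "Complete baseline symptom survey to establish severity of symptoms (if present"). The synopsis adds, for symptomatic participants, "The date of onset of the first of the above symptoms will be documented". Sections 5.1 and 7.1 do not mention the onset date.

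Neither item enters the primary model or a named sensitivity analysis. Section 9.6 does use all baseline characteristics, but only in the imputation model. The introduction to section 9 leaves complete analysis details to a formal SAP, due after study initiation.

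**The concern.** Time from randomization to clearance may depend on how far along the infection is at entry. One participant may be asymptomatic, another newly ill and a third well into the illness. Section 9.2 assumes that 33% of participants are already PCR-negative on Day 1 despite a recent positive swab, which fits a wide spread of stages at entry.

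In a Cox model, leaving out a prognostic baseline variable lowers the power of the treatment test, even under randomization. With about 120 participants expected to inform the primary comparison, that could matter. The protocol already intends to collect the two variables that bear most directly on illness stage, so any gain is available without new assessments.

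**Working it through.** **The plan's own figure.** Section 9.2 states that 79 events give 80% power at a hazard ratio (HR) of 2.03, with 1:1 allocation and a "two-sided log rank test" at alpha 0.04999. With (1.960 + 0.842)² = 7.85:

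- Schoenfeld: events = 4 × 7.85 / (ln 2.03)² = 31.4 / 0.501 = 62.6, so 63.
- Freedman: events = 7.85 × (3.03 / 1.03)² = 67.9, so 68.

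The 79 is not reproduced. At HR 2.03, 79 events give 88.2% (Schoenfeld) or 85.6% (Freedman). By Schoenfeld, 79 events give 80% power at HR 1.88. This discrepancy is on the conservative side and is a separate matter. It is why the runs below use HR 1.88 as well as 2.03, and why power with no prognostic effect is near 87% rather than 80%.

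**Simulation A: the two proposed covariates.**

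- From section 9.2: 120 participants (60 per arm), exponential times with control median 14 days, 10% control dropout, alpha 0.04999.
- Assumed, because the documents are silent: 80% symptomatic; standard-normal onset time among the symptomatic; the same prognostic hazard ratio h for symptomatic versus asymptomatic and per SD of onset time.
- Follow-up cut at 16.5 days, so that about 79 events occur (77 to 81 across rows). 4,000 runs per row; Monte Carlo standard error about 0.5 to 0.8 points.

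| True HR | h | Power without | Power with | Gain (points) | Mean HR without | Mean HR with |
|---|---|---|---|---|---|---|
| 2.03 | 1 | 87.5% | 87.1% | −0.4 | 2.04 | 2.05 |
| 2.03 | 1.25 | 86.4% | 87.5% | 1.1 | 2.01 | 2.06 |
| 2.03 | 1.5 | 82.7% | 87.5% | 4.8 | 1.94 | 2.06 |
| 2.03 | 2 | 71.6% | 86.7% | 15.1 | 1.80 | 2.05 |
| 1.88 | 1 | 78.9% | 78.8% | −0.1 | 1.89 | 1.90 |
| 1.88 | 1.25 | 77.2% | 79.0% | 1.8 | 1.86 | 1.91 |
| 1.88 | 1.5 | 73.9% | 79.5% | 5.6 | 1.81 | 1.91 |
| 1.88 | 2 | 62.3% | 77.5% | 15.2 | 1.70 | 1.91 |

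With a true HR of 1 (1,500 runs per row, 14 days of follow-up), rejection rates were 4.1% to 5.9% with or without the covariates.

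**Simulation B: the swab calendar.** Clearance read at Days 1 to 10, 14, 21 and 28 with the two-negative rule, Efron ties, 60 per arm, 10% control dropout and one perfectly measured standard-normal covariate. 1,000 runs per row.

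| True HR | Prognostic HR per SD | Power without | Power with | Gain (points) |
|---|---|---|---|---|
| 2.0 | 1 (none) | 89.9% | 89.8% | −0.1 |
| 2.0 | 1.3 | 85% | 87% | 2 |
| 2.0 | 1.6 | 82% | 89% | 7 |
| 2.0 | 2.0 | 73% | 88% | 15 |
| 1.75 | 1.3 | 68% | 71% | 3 |
| 1.75 | 1.6 | 66% | 74% | 8 |
| 1.75 | 2.0 | 54% | 69% | 15 |

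**Simulation C: an imperfect proxy.** Same calendar, HR 2.0, 1,500 runs per row. The recorded covariate correlates only partly with true illness stage; the correlations are assumptions. Gains at 1.3 / 1.6 / 2.0 per SD of true stage:

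- perfect measurement: about 1 / 8 / 14 points;
- correlation 0.5: about 0 / 1 / 4 points, with adjusted HR 1.96 / 1.89 / 1.82;
- correlation 0.3: about 0 / 1 / 1 points.

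**Limits.** None of these runs includes site strata, age or sex. All cover only the 120 participants assumed PCR-positive on Day 1, whereas section 9.4 places efficacy analyses in all 180 randomized.

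**The case against.** The planned model is a standard prespecified choice: it adjusts for both randomization factors and stratifies by site. Nothing in the documents shows that symptom status or onset date predicts PCR clearance. With no association, nothing is lost. Days since onset says nothing about infection stage in asymptomatic participants, so the larger gains are best cases. Onset date appears only in the synopsis, so its capture is not assured. All of this stands. It limits the claim about size but does not argue against adjusting, because the cost is close to nil when the covariates prove uninformative.

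A reader might infer three stronger things that the documents do not support.

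- *The planned hazard ratio is biased toward 1, or the test is invalid.* The lower hazard ratio without the covariates is non-collapsibility: the less-adjusted model estimates a different, more marginal quantity. The test keeps its type I error, and randomization-based inference already allows for chance imbalance.
- *The trial is known to be losing power or to fall short of 80%.* The simulations fix the covariate-adjusted hazard ratio and assume the prognostic strength. If 2.03 is read as the hazard ratio that the less-adjusted model would estimate, the planned power is not reduced and adjustment could only add to it.
- *The 33% assumed PCR-negative on Day 1 shows that stage predicts clearance.* It is consistent with varied stages at entry, but does not measure how well onset date predicts anything.

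**Conclusion.** The point holds as a missed efficiency gain in a valid analysis. At a hazard ratio of about 2 in 120 participants PCR-positive on Day 1, prespecifying the two covariates would add about 0 to 3 points of power if they are weak predictors or poor proxies for illness stage (4 in one row, where a strong stage effect is seen through a proxy correlated 0.5). It would add about 5 to 8 points if they are moderate predictors, and up to about 15 if strong and well measured. If they are not prognostic, the loss is within simulation error.

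Where in that range the trial lies cannot be determined from the documents, and the figures do not carry over to the full 180-patient analysis. The change is worth making because the downside is near zero, not because a particular gain has been shown.

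**What to change.** In section 9.6 and the synopsis, add two prespecified covariates to the primary Cox model:

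- symptomatic versus asymptomatic at baseline;
- days from first symptom to randomization, set to 0 for asymptomatic participants, with the symptom indicator kept in the model.

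Keep age, sex and stratification by site. List date of first symptom as a Day 1 pre-dose item in section 7.1. Have blinded staff fix the model before any unblinding, and apply it to both interim and final analyses, since section 10 has the interim use the final methods. Do not make a Day 1 quantitative PCR value a covariate conditional on whether the laboratory happens to keep it; that would leave the primary model undefined in advance.

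The cost is one or two degrees of freedom, a short text change in three places, and a check that onset date is actually captured in the case report form.
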